11.3 Statistical Methods

For the cognitive measures, the scores will be transformed to z scores to adjust for age: Each individual IIV value will be transformed into an age-normative z score using the Cogstate normative database (n=95,162). This will result in an age-adjusted IIV z score for use in all analyses described below.

BICAMS tests of SDMT, RAVLT and BVMT-R will be similarly converted to age-normative z scores using the most recently available databases¹³³⁻¹³⁶. A single BICAMS score will be computed as the average of z scores across the three measures⁴⁹.

Baseline patient and disease characteristics will be summarized for the 60 participants enrolled into this cohort. The primary focus in this cohort is to evaluate IIV along with changes in CMRO₂ during stimulation as described above as predictors of disease status. Distributions of IIV values and CMRO₂ at baseline and during stimulation, along with changes in CMRO₂ will be summarized descriptively and graphically with BICAMS classes. Bivariate scatterplots will display the baseline, during, and changes with IIV levels. Pairwise correlations will be estimated as measures of association between these variables (with transformations of values if required). Based on prior data, the mean change from baseline in CRMO₂ in 31 patients =7.91, sd=10.17 (mean % change =5.61%, sd=6.72). Here, we will predict IIV based on the CMRO₂ measurements at baseline and in response to tDCS. Other covariates will be incorporated into these exploratory models. For the binary BICAMS classes, again AUCs for the ROC curves from logistic models will be used to evaluate the roles of CRMO₂ changes and IIV. Sample size. With 50 evaluable participants, we can detect an R² \geq 0.141 from a univariable regression model and of 0.225 with 5 independent variables. The collected data for this prodromal cohort will serve as the basis for future longitudinal follow-up of this cohort.

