11.2 Sample Size Determination

We aim to enroll 60 participants with prodromal MS to have n=50 evaluable participants (30 evaluable for the tDCS-MRI group and 20 evaluable for cognitive assessment group). As this is an exploratory protocol that is collecting data for future power analyses, the designation of recruiting 60 human subjects is arbitrary. Showing the feasibility of using Cogstate by this initial sample of participants, future studies can be conducted with properly powered samples to build a larger database. Recruitment of 60 participants would allow for enough data for assessing feasibility.

CONFIDENTIAL

This material is the property of the NYU Langone. Do not disclose or use except as authorized in writing by the study sponsor
Observational Study Template Version: 8 February 2019

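### BICAMS is scored on a continuous scale, but its only named outcome model is a logistic AUC on two classes, and the stated detectable R² does not hold for the roughly 30 people with CMRO₂

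*Combined protocol and SAP*

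**What the plan says.** Section 11.3 (Statistical Methods) converts SDMT, RAVLT and BVMT-R to age-normative z scores, and then "A single BICAMS score will be computed as the average of z scores across the three measures". The result is continuous. After that, BICAMS appears only as classes. IIV and CMRO₂ values "will be summarized descriptively and graphically with BICAMS classes", and the outcome model reads "For the binary BICAMS classes, again AUCs for the ROC curves from logistic models will be used to evaluate the roles of" CMRO₂ change and IIV. No rule turns the mean z into two classes, and no interval for the AUC is mentioned. The correlations and the other regression in that section concern IIV and CMRO₂.

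The section also says "The primary focus in this cohort is to evaluate IIV along with changes in" CMRO₂. Its one precision statement is for 50 evaluable participants: a detectable R² of 0.141 "from a univariable regression model and of 0.225 with 5 independent variables". Section 11.2 splits those 50 into "30 evaluable for the tDCS-MRI group and 20 evaluable for cognitive assessment group", and Section 6.6 gives the same targets.

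The Protocol Summary lists BICAMS as a secondary outcome and names correlation and regression in general terms. Section 4.2 sets a secondary objective of exploring how IIV relates to cognitive function.

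**The concern.** Splitting a continuous score into two classes discards information, and in 30 to 50 people there is little to spare. A real link between IIV, or the CMRO₂ response, and cognition is then more likely to be missed. The loss is avoidable because the continuous score is computed anyway.

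The second issue is the sample behind the precision figures. CMRO₂ is measured only in the tDCS-MRI group, so a figure based on 50 people is too favourable for any model that contains it.

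What is at stake is the quality of the estimates carried forward. Section 11.2 gives the purpose: "As this is an exploratory protocol that is collecting data for future power analyses". Section 11.3 adds: "The collected data for this prodromal cohort will serve as the basis for future longitudinal follow-up of this cohort". An imprecise AUC reported without an interval is a poor basis for sizing the next study.

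**Working it through.** **Inputs from the documents.** Evaluable n=50 overall and n=30 with CMRO₂ (Sections 11.2 and 6.6); R² of 0.141 and 0.225 (Section 11.3).

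**Assumptions.** Two-sided α=0.05 and 80% power, which are not stated with the R² figures. An impaired share of 20–50%, because no cut-off is given. Marker and BICAMS score bivariate normal. Power here means the chance that a two-sided 5% test shows an association; the plan names no test for BICAMS.

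**1. Reproduce the plan's figures.** Overall F test in linear regression with p predictors, degrees of freedom (p, n−p−1), noncentrality λ = n·R²/(1−R²). Solving for 80% power:
- n=50: R² = 0.1405 (p=1) and 0.2251 (p=5). Both match the plan.
- n=30: R² = 0.219 (p=1), 0.264 (p=2), 0.349 (p=5).
- R²=0.141 with one predictor: λ = 50×0.141/0.859 = 8.2 and power 0.80 at n=50; λ = 30×0.141/0.859 = 4.9 and power 0.57 at n=30.

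**2. Information kept by the class.** With a share s impaired and z the normal quantile at s, the fraction kept is φ(z)²/[s(1−s)]. For 20% this is 0.280²/0.16 = 0.490; for 50%, 0.399²/0.25 = 0.637. An R² of 0.141 therefore behaves roughly like 0.141×0.490 = 0.069 to 0.141×0.637 = 0.090, below what 50 people can detect.

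**3. Power by simulation** (8,000 data sets per setting, r = √0.141 = 0.375). Pearson correlation with the continuous score gives 0.77–0.78 at n=50 and 0.55–0.56 at n=30. These are slightly below step 1 because the predictor is random rather than fixed.

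| Assumed share impaired | 20% | 30% | 40% | 50% |
|---|---|---|---|---|
| Information kept | 0.490 | 0.576 | 0.622 | 0.637 |
| Class, rank test, n=50 | 0.436 | 0.501 | 0.538 | 0.541 |
| Class, likelihood ratio, n=50 | 0.482 | 0.549 | 0.590 | 0.593 |
| Class, rank test, n=30 | 0.256 | 0.309 | 0.326 | 0.345 |
| Class, likelihood ratio, n=30 | 0.324 | 0.375 | 0.387 | 0.408 |
| AUC 95% half-width at 0.70, n=50 | 0.196 | 0.167 | 0.153 | 0.146 |
| AUC 95% half-width at 0.70, n=30 | 0.255 | 0.217 | 0.198 | 0.189 |

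A separate simulation of the n=50 rank test gave 0.427–0.549, hence the range of 43–55%. If only 10% are impaired, rank-test power is about 0.30 (n=50) and 0.16 (n=30).

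**4. AUC precision** (last two rows). Hanley–McNeil: SE² = [A(1−A) + (m−1)(Q₁−A²) + (k−1)(Q₂−A²)]/(mk), with Q₁ = A/(2−A), Q₂ = 2A²/(1+A), m impaired and k not. For A=0.70, m=6, k=24: (0.21 + 5×0.0485 + 23×0.0865)/144 = 0.0170, SE = 0.130, half-width 1.96×0.130 = 0.255.

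**5. Optimism of the AUC.**
- One marker, direction fixed in advance: the AUC of a worthless marker averages 0.50. With direction free it averages 0.59–0.61 at n=30.
- One marker with R²=0.141, direction free: optimism is at most 0.004 at n=50 and about 0.00–0.01 at n=30.
- Two worthless markers fitted jointly at n=30: mean apparent AUC 0.63–0.67.
- A worthless CMRO₂ term added to a real IIV marker (R²=0.141) at n=30: mean AUC rises from 0.698 to 0.742 (20% impaired) or from 0.676 to 0.707 (50%). The gain is 0.05 or more in 24–32% of samples.
- After bootstrap correction (smaller check, 300 data sets) the mean gain is −0.009 to −0.004, but a gain of 0.05 or more still appears in 14–16% of samples.

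**The case against.** The study is exploratory, BICAMS is a secondary outcome and no rule depends on the AUC. The class also answers a question of its own: Section 11.1 speaks of a clinical classification, for its first aim, and Section 11.3 of predicting disease status. Comparing its power with that of a continuous model therefore compares two questions. This stands. It is why the class AUC should be kept, and why the point is modest.

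Three stronger readings are tempting, and the documents do not support them.

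- *That the plan excludes a continuous BICAMS analysis.* It does not. The Protocol Summary lists correlation and regression, and Section 4.2 would accommodate such a model. It is simply not specified.
- *That the R² figures are wrong, or are offered as covering the AUC.* They reproduce, and the text ties them to regression. The gap is that they assume 50 people. That bears as much on the planned regression of IIV on CMRO₂ as on BICAMS.
- *That the single-marker AUC would be badly inflated.* At R²=0.141 the optimism is about 0.01 or less. Section 11.1 also states a direction for IIV (for the first aim), and fixing it in advance removes the optimism of a worthless marker. Optimism matters mainly if IIV and CMRO₂ change enter one logistic model, which the wording suggests but does not say.

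The unstated cut-off, the unstated interval and the joint-or-separate question are missing detail rather than errors. The word "again" in the AUC sentence may point to a fuller text elsewhere.

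**Conclusion.** The point holds in two parts. First, as specified, the BICAMS analysis uses only the class. At R²=0.141 this has about 43–55% power against 78% for the continuous score at n=50, and about 26–35% against 55% at n=30. These figures assume 20–50% impaired, bivariate normality and a rank test; a likelihood-ratio test narrows the gap by about five to seven percentage points but does not close it. Second, models with CMRO₂ can detect an R² of about 0.22, 0.26 or 0.35 with one, two or five predictors, not 0.141 or 0.225.

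Both parts concern efficiency and correct labelling of precision. A reader might infer that the study's conclusions are at risk. They are not: no decision rests on this analysis, and the effect is on estimates used to plan later work.

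**What to change.** In Section 11.3:

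1. Add linear regression of the continuous BICAMS mean z on IIV (about 50 people) as the main BICAMS analysis. Add supporting models on CMRO₂ change and on both (about 30 people). Give a 95% confidence interval for each.
2. Keep the class AUC as the clinical reading. State the cut-off, fix the direction for IIV in advance and report a 95% confidence interval. State the expected half-width at an AUC of 0.70: about 0.15–0.20 at n=50 and 0.19–0.26 at n=30.
3. Say whether the logistic models are separate or joint. Only if joint, apply bootstrap optimism correction and compare with IIV alone in the same 30 people. Note the limits: a useless marker can still show an apparent gain, and the correction is unstable when few are impaired. With 3 impaired of 30, 0.9³⁰ = 4% of resamples contain none, and 18% contain fewer than two.
4. State that R² of 0.141 and 0.225 applies to linear models in 50 people without CMRO₂, and give about 0.22, 0.26 and 0.35 (one, two and five predictors) for models with CMRO₂ in 30.

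The cost is a few lines of text and code, with no new data. The stated figures become less favourable and the intervals are wide. The linear model in 30 people remains weak, at about 55% power for R²=0.141.

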5.1 Description of Study Design

We will recruit 60 participants over a two-year period to assess the feasibility of developing the measurement of IIV towards its clinical application as prodromal marker of MS, and to test the association between IIV and the real-time neuronal responses to tDCS as prodromal MS marker via a tDCS-MRI scan.

Thirty-five (35) participants will complete 1 visit that will last approximately 3.5 hours. The visit will include consent, a cognitive assessment, an optional gait assessment, and a 1-hour MRI brain scan combined with 20 minutes of simultaneous tDCS. Participants may also complete the MRI on a separate visit.

Twenty-five (25) participants will complete 1 visit that will last approximately 1.5 hours (consent, cognitive assessment, and optional gait assessment). Procedures are exactly the same except that the tDCS-MRI will not be completed.

Group assignment will depend on eligibility, enrollment space (e.g. if one group reaches its target), and participant choice. The only difference between the two groups is that 1 group will have the MRI-tDCS procedure.

CONFIDENTIAL

This material is the property of the NYU Langone. Do not disclose or use except as authorized in writing by the study sponsor
Observational Study Template Version: 8 February 2019

6 Study Enrollment and Withdrawal

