6.6 Total Number of Participants and Sites

This study will recruit a total of 60 participants (target for participants who complete the tDCS-MRI is n=30 and target for participants who complete the cognitive assessment only is n=20 for total target of n=50, plus 10 to account for screen fails and withdrawals) at NYU Langone Health.

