11.3.1 Agency for Healthcare Research and Quality (AHRQ) Indicator

An additional feature of our analyses is the inclusion of environmental adversity represented by socioeconomic status (SES). For all participants, using the zip code of their home residence, we will use the AHRQ indicator as a single linear value of SES and quality of healthcare access. This indicator will provide secondary and exploratory testing of the role of SES in IIV and clinical disability benchmarks.

12 Source Documents and Access to Source Data/Documents

Source data is all information, original records of clinical findings, observations, or other activities in a study necessary for the reconstruction and evaluation of the study. Source data are contained in source documents. Examples of these original documents, and data records include: hospital records, clinical and office charts, laboratory notes, memoranda, subjects' diaries or evaluation checklists, pharmacy dispensing records, recorded data from automated instruments, copies or transcriptions certified after verification as being accurate and complete, microfiches, photographic negatives, microfilm or magnetic media, x-rays, subject files, and records kept at the pharmacy, at the laboratories, and at medico-technical departments involved in the study.

The study case report form (CRF) is the primary data collection instrument for the study. All data requested on the CRF must be recorded. All missing data must be explained. If a space on the CRF is left blank because the procedure was not done or the question was not asked, write "N/D". If the item is not applicable to the individual case, write "N/A". All entries should be printed legibly in black ink. If any entry error has been made, to correct such an error, draw a single straight line through the incorrect entry and enter the correct data above it. All such changes must be initialed and dated. DO NOT ERASE OR WHITE OUT ERRORS. For clarification of illegible or uncertain entries, print the clarification above the item, then initial and date it.

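### The detectable R² in section 11.3 is worked out for 50 participants, but the regression described there needs CMRO2, which only 30 evaluable participants will have

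*Combined protocol and SAP*

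**What the plan says.** The sample-size statement in section 11.3 reads "With 50 evaluable participants, we can detect an" R² of at least "0.141 from a univariable regression model and of 0.225 with 5 independent variables". It does not say which outcome or predictors are meant, or at what alpha and power.

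Earlier in the same paragraph, the section sets out its regression: "Here, we will predict IIV based on the CMRO₂ measurements at baseline and in response to tDCS". It adds: "Other covariates will be incorporated into these exploratory models". The other model there is logistic, for binary BICAMS class, and also uses CMRO2 change.

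CMRO2 is an MRI measurement (section 8.3). Section 11.2 divides the 50 evaluable participants into "30 evaluable for the tDCS-MRI group and 20 evaluable for cognitive assessment group", and section 6.6 gives the same split: "target for participants who complete the tDCS-MRI is n=30 and target for participants who complete the cognitive assessment only is n=20". Section 5.1 says of the second group: "Procedures are exactly the same except that the tDCS-MRI will not be completed". It enrols 35 participants with MRI and 25 without.

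**The concern.** Twenty of the 50 participants behind the R² figures will have no CMRO2 value by design. They cannot enter the regression that the paragraph has just described. No section gives a detectable R² for 30.

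The Protocol Summary lists CMRO2 as a primary outcome, and section 11.3 makes IIV together with CMRO2 change the main focus of the cohort. The R² sentence is the plan's only quantitative statement of sensitivity. A reader will naturally take 0.141 as the smallest CMRO2–IIV association the study can reliably detect. A null CMRO2 result could then be read as evidence against true associations with R² between about 0.14 and 0.22, which the study would detect with less than 80% power.

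The point is limited to linear regression. R² does not directly give the sensitivity of the high-versus-low IIV contrast in section 11.1 or of the ROC analyses, and the plan gives no figure for either.

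**Working it through.** **Inputs**

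- n = 50 evaluable; detectable R² 0.141 (one predictor) and 0.225 (five): section 11.3.
- n = 30 evaluable with MRI: sections 6.6 and 11.2.
- n = 35 enrolled for MRI: section 5.1 (best case, no losses).
- Alpha and power: not stated with the figures, so inferred in step 1.

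**Method.** Overall F test of R² = 0 with k predictors. Degrees of freedom are k and n − k − 1, and the noncentrality is λ = n·R²/(1 − R²). Power is the probability that a noncentral F exceeds the critical F. The detectable R² is the value at which power equals the target.

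**Step 1: reproduce the plan's figures.** With n = 50, alpha 0.05 and power 0.80:

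- k = 1: df 1 and 48, critical F 4.043. The solution is R² = 0.1405, with λ = 50 × 0.1405/0.8595 ≈ 8.17. Stated: 0.141.
- k = 5: df 5 and 44, critical F 2.427. The solution is R² = 0.2251, with λ = 50 × 0.2251/0.7749 ≈ 14.52. Stated: 0.225.

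Twelve combinations were tried (alpha 0.01, 0.025, 0.05, 0.10 with power 0.80, 0.85, 0.90). Only 0.05 with 0.80 reproduces both figures. The next closest, 0.10 with 0.90, gives 0.150 and 0.235. The same formula at n = 60 gives 0.119 and 0.191, so the plan did use 50.

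**Step 2: repeat with the participants who have CMRO2.** Alpha 0.05, power 0.80:

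| Predictors | n = 50 | n = 35 | n = 30 |
|---|---|---|---|
| 1 | 0.1405 | 0.1923 | 0.2192 |
| 2 | 0.1705 | 0.2324 | 0.2645 |
| 5 | 0.2251 | 0.3065 | 0.3488 |

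The two-predictor row is the regression as described, with CMRO2 at baseline and its response to tDCS. For one predictor, |r| = √R²: √0.1405 = 0.375 at n = 50, √0.1923 = 0.438 at n = 35 and √0.2192 = 0.468 at n = 30.

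**Step 3: power for the effects the plan states**

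| Effect | n = 50 | n = 35 | n = 30 |
|---|---|---|---|
| R² = 0.141, k = 1 | 80.2% | 64.3% | 57.2% |
| R² = 0.225, k = 5 | 80.0% | 59.1% | 49.9% |

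At n = 30, λ for the first row is 30 × 0.141/0.859 = 4.92, against 8.21 at n = 50.

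**Step 4: sensitivity to the method.** The formula treats predictors as fixed, whereas CMRO2 is measured and varies at random. A random-predictor calculation at n = 30 gives 0.235 (k = 1) and 0.371 (k = 5), slightly worse. Simulation with random normal predictors (20,000 runs each) puts power for the stated effects at 0.55 and 0.47 at n = 30, and 0.78 and 0.77 at n = 50. The conclusion does not depend on this choice.

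**The case against.** The sentence never mentions CMRO2. It gives its own n, and section 11.2 has just shown how the 50 divide. Read strictly, it may describe models that all 50 can enter, such as IIV with BICAMS or with the socioeconomic indicator, of which section 11.3.1 says: "This indicator will provide secondary and exploratory testing of the role of SES in IIV and clinical disability benchmarks". The plan does not use the word linear for the CMRO2 regression, and section 11.1 frames the same aim as separating high from low IIV. Section 11.2 also calls the protocol exploratory and its enrolment number arbitrary, and no decision rule rests on 0.141. Future power analyses would draw on this study's estimated effects and variances, not on its detectable R².

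Much of this stands, and it limits the severity. The n = 50 figures are valid for models without CMRO2. But section 11.3 writes out no such linear model, and section 11.3.1 gives no model for the socioeconomic indicator. IIV enters the analyses as a continuous z score, so linear regression is the natural reading, and an R² figure presupposes it. An exploratory label does not make a figure apply to participants who lack the measurement.

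**Conclusion.** The point holds. The calculation is correct for 50, but that number does not fit the only linear regression the section describes, and the text does not say which models the figures cover. For CMRO2 models the detectable R² is 0.22, 0.26 and 0.35 with one, two and five predictors. The plan states 0.141 with one and 0.225 with five. With all 35 MRI participants evaluable it would be 0.19, 0.23 and 0.31, so no planned MRI number reaches the stated figures.

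This rests on alpha 0.05 and 80% power, inferred because they reproduce both figures, and on reading the CMRO2 model as linear in IIV. All values are whole-model R²; they are not the share that CMRO2 must explain beyond other covariates. The statement should be fixed, but it does not undermine the design.

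**What to change.** Replace the sample-size sentence in section 11.3 with:

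> Detectable R² (whole model, overall F test) is given for alpha 0.05 and 80% power [study statistician to confirm]. For models containing CMRO2 (30 evaluable participants) it is 0.22 with one predictor, 0.26 with two and 0.35 with five. For models without CMRO2 (50 evaluable participants; for example IIV with BICAMS or the SES indicator) it is 0.141 with one predictor and 0.225 with five. These figures do not apply to the ROC analyses.

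The BICAMS and SES models are only examples. The plan does not yet write them out as linear regressions, so the statistician should keep them only if they are intended.

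The cost is a wording change. The stated sensitivity for CMRO2 becomes less favourable. Planned covariates, models and enrolment stay as they are.

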11.1 Study Hypotheses

For the first aim with a cross-sectional representative cohort data, we hypothesized that higher IIV predicts a clinical classification of early cognitive impairment. For the second aim with longitudinal observational early MS cohort, we predict that higher IIV at baseline will predict greater decline. For the last aim with prospective recruitment of a prodromal cohort, we predict that that CMRO₂ response to tDCS to DLPFC will differentiate at-risk patients with high vs. low IIV.

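### The detectable R² of 0.225 in section 11.3 describes a five-variable model as a whole at n=50; it is not the detectable effect for the CMRO₂ response, which only 30 evaluable participants will have

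*Combined protocol and SAP*

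**What the plan says.** For the prospectively recruited cohort, section 11.1 predicts that the "CMRO₂ response to tDCS to DLPFC will differentiate at-risk patients with high vs. low IIV". Section 11.3 turns this into a regression in which "we will predict IIV based on the CMRO₂ measurements at baseline and in response to tDCS", and adds that "Other covariates will be incorporated into these exploratory models". Those covariates are neither named nor counted. Section 11.3.1 brings in an area-level socioeconomic indicator, as secondary and exploratory, to examine its role in IIV.

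The same paragraph of section 11.3 closes with the sensitivity statement: "With 50 evaluable participants, we can detect an R² \geq 0.141 from a univariable regression model and of 0.225 with 5 independent variables". It gives no alpha, power or test, and does not say which five variables are meant. Section 11.2 splits the 50 evaluable participants into "30 evaluable for the tDCS-MRI group and 20 evaluable for cognitive assessment group". The same section describes the protocol as exploratory and the recruitment number of 60 as arbitrary.

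**The concern.** Two things do not fit. First, a detectable R² for a model with five predictors normally refers to the joint test that all five coefficients are zero. That differs from asking whether the CMRO₂ response is related to IIV once baseline CMRO₂ and covariates are in the model. If 0.225 is the joint-test figure, the plan gives no detectable effect for the adjusted form of its own hypothesis.

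Second, any model that contains CMRO₂ can use only participants who were scanned. A figure computed at n=50 cannot apply to it.

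At stake is what the study can claim about its sensitivity, and what it passes on. Section 11.2 says the data will feed future power calculations. Those need the effect of the response term, not an R² mixed with whatever the covariates explain. A reader could also take a sizeable overall R² as evidence about the response when other variables produced it.

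**Working it through.** **Inputs.** From section 11.3: n = 50, R² = 0.141 (1 variable) and 0.225 (5 variables). From section 11.2: 30 evaluable participants in the tDCS-MRI group. Not in the documents, hence assumed: alpha 0.05 and power 0.80.

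**Method.** For a model with p predictors and a test on q of them, the statistic is F with q and n − p − 1 degrees of freedom. Its noncentrality is λ = n·R²/(1 − R²), where R² is the whole-model value if q = p and the partial value if q < p. Find the λ that gives 80% power, then R² = λ/(n + λ).

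**Step 1: reproduce the plan's figures (n = 50, q = p).**
- p = 1: df 1 and 48, critical F 4.043, λ = 8.175, R² = 8.175/58.175 = 0.1405. Stated: 0.141.
- p = 5: df 5 and 44, critical F 2.427, λ = 14.522, R² = 14.522/64.522 = 0.2251. Stated: 0.225.

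Both figures match under one set of assumptions. Alternatives miss: for p = 5, alpha 0.10 with 80% power gives 0.188, alpha 0.05 with 90% power gives 0.272, and alpha 0.10 with 90% power gives 0.235. So 0.225 is the joint test of all five coefficients.

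**Step 2: put the question to the response term (five-variable model, n = 50).**
- Response only, q = 1: df 1 and 44, λ = 8.206, partial R² = 8.206/58.206 = 0.141.
- Baseline and response together, q = 2: λ = 10.322, partial R² = 10.322/60.322 = 0.171.

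Neither gives 0.225.

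**Step 3: use the N that has CMRO₂ (n = 30).**

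| Test | df | λ | Detectable R² |
|---|---|---|---|
| One-variable model | 1, 28 | 8.424 | 0.219 |
| Overall, five variables | 5, 24 | 16.067 | 0.349 (whole model) |
| Response term in five-variable model | 1, 24 | 8.527 | 0.221 (partial) |
| Baseline and response in five-variable model | 2, 24 | 10.946 | 0.267 (partial) |

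At n = 30 the overall test has 50% power at R² = 0.225, against 80% at n = 50. The one-variable test has 57% power at R² = 0.141.

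The closeness of 0.221 to the printed 0.225 is a coincidence. One is a partial R² on 1 df at n = 30; the other is a whole-model R² on 5 df at n = 50.

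**Step 4: scale.** A partial R² becomes an R² increment on multiplying by (1 − R² of the other four variables). The documents give no value for the latter. Over an assumed 0 to 0.30, the detectable increment at n = 30 runs from 0.221 to 0.2213 × 0.70 = 0.155.

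**Step 5: why the two tests should be kept apart.** Suppose CMRO₂ contributes nothing and the covariates alone explain an assumed 10%, 15% or 22.5% of IIV variance. The overall test is then significant with probability 36%, 55% or 80% at n = 50, and 20%, 31% or 50% at n = 30. In a simulation of 20,000 runs at covariate R² of 22.5%, with independent predictors, the 1-df test of a CMRO₂ term rejected about 5% of the time at either n. This shows what the overall test responds to; it is not an error rate of the plan.

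**The case against.** A reader might infer that the plan will treat a significant five-variable model as support for the tDCS-response hypothesis, and that covariates could therefore produce a false positive with the probabilities in step 5. The documents do not support this. Section 11.3 states no null hypothesis, criterion or decision rule, and it calls the models exploratory. The misreading is possible but not planned. Those probabilities also rest on assumed covariate R² values, and the 22.5% case largely restates the 80% power of the joint test. Because IIV is already an age-normative z score, one obvious covariate has mostly been removed.

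Nor was the study sized on this test: section 11.2 calls the number arbitrary, and 0.225 is a sensitivity figure at a fixed N.

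It can also be said that section 11.3 examines response against IIV directly, through scatterplots, pairwise correlations and the univariable figure. That is so, but those assessments are unadjusted, and the univariable 0.141 also assumes 50 participants. At n = 50 the response-specific figure (0.141) is smaller than 0.225, so the joint-test figure alone does not overstate sensitivity. The shortfall comes from n = 30.

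Finally, baseline CMRO₂ is itself a named predictor, and section 11.1 speaks of high versus low IIV, so a single linear coefficient is one way to express the hypothesis, not the only one. This stands. It is a reason to name the term tested, and the 2-df figure is given above for a joint CMRO₂ test.

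**Conclusion.** The point holds as a mis-specified sensitivity statement. The 0.225 is the whole-model detectable R² at n = 50. It is not the detectable effect for the CMRO₂ response, and it is not attainable for a model containing CMRO₂ at the stated power. With 30 evaluable scans the whole-model figure is about 0.35, and the response-specific partial R² is about 0.22.

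This rests on alpha 0.05 and 80% power, which are inferred from the match to both printed figures, and on exactly five predictors with all 30 scans usable. The conclusion does not extend to a claim that the planned inference is invalid or that the study was sized on the wrong test. In an exploratory protocol the consequence is a wrong benchmark and an opening for misinterpretation, which is worth correcting before analysis.

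**What to change.** In section 11.3:

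1. Replace the five-variable figure with the detectable partial R² for the CMRO₂-response term at the N with CMRO₂: about 0.22 at n = 30 in a five-variable model, 1 df. If the overall figure is kept for context, give it as about 0.35 at n = 30. State alpha and power, and name the covariates.
2. State that the adjusted assessment of the section 11.1 hypothesis is the CMRO₂-response coefficient, reported with a 95% CI and its incremental R² over baseline CMRO₂ and the covariates. Label overall model R² as descriptive.
3. Keep n = 50 only for models that do not contain CMRO₂. If the univariable figure is meant for a CMRO₂ predictor, it becomes 0.219 at n = 30.

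The cost is a few sentences, with no new data, participants or procedures. The small downside is that a high overall R² could no longer be presented as support for the response hypothesis.
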